6.1.4.1 Erythroid response (HI-E)

Major response: For patients with pretreatment hemoglobin less than 11 g/dL, greater than 2 g/dL increase in hemoglobin; for RBC transfusion-dependent patients, transfusion independence.

Minor response: For patients with pretreatment hemoglobin less than 11g/dL, 1 to 2 g/dL increase in hemoglobin; for RBC transfusion-dependent patients, 50% decrease in transfusion requirements.

6.1.4.2 Platelet response (HI-P)

Major response: For patients with a pretreatment platelet count less than 100×10^9 /L, an absolute increase of 30×10^9 /L or more; for platelet transfusion-dependent patients, stabilization of platelet transfusion independence.

Minor response: For patients with a pretreatment platelet count less than $100x10^9/L$ a 50% or more increase in platelet count with a net increase greater than $10 \times 10^9/L$ but less than $30 \times 10^9/L$

6.1.4.3 Neutrophil response (HI-N)

Major response: For absolute neutrophil count (ANC) less than 1.5×10^9 /L before therapy, at least a 100% increase, or an

absolute increase of more than $0.5 \times 10^9/L$, whichever is greater.

Minor response: For ANC less than 1.5×10^9 /L before therapy, ANC increase of at least 100%, but absolute increase less than 0.5×10^9 /L.

6.1.4.4 Progression/relapse after HI

One or more of the following: a 50% or greater decrement from maximum response levels in granulocytes or platelets, a reduction in hemoglobin concentration by at least 2 g/dL, or transfusion

6.2 CML response criteria

6.2.1 Hematologic Response (HR)

- 1. Complete Hematologic Response (CHR):
 - a. WBC ≤ institutional upper limit of normal (ULN)
 - b. Platelets $\leq 450.000 \times 10^9 / L$
 - c. No blasts or promyelocytes in peripheral blood.
 - d. < 5% myelocytes plus metamyelocytes in peripheral blood
 - e. Peripheral blood basophils < 2%
 - f. No extra-medullary involvement including no splenomegaly or hepatomegaly
 - q. <5% blasts in bone marrow
- 2. No Evidence of Leukemia (NEL) meet the same criteria as CHR except for:
 - a. Platelets ≥ 20.000/mm3 and < 100.000 mm3, and/or
 - b. ANC > 500/mm3 and < 1,000/mm3
- 3. Minor Hematologic Response (MiHR) meet all of the following:
 - c. < 15% blasts in BM and in PB
 - d. < 30% blasts + promyelocytes in BM and PB
 - e. < 20% basophils in PB
 - f. No extra-medullary disease other than spleen and liver
- 4. Major Hematologic Response (MHR) is defined as CHR or NEL
- 5. Overall Hematologic Response (OHR) is defined as CHR, NEL or MiHR

A **confirmed** HR is obtained when all above criteria are fulfilled at least 28 days after they are first met.

6.2.2 Cytogenetic Response (CyR):

Classified according to suppression of the Philadelphia chromosome (Ph) by cytogenetics (FISH if cytogenetic analysis not informative, e.g., insufficient metaphases)

- 1. No cytogenetic response Ph positive >95%
- 2. Minimal cytogenetic response Ph positive 66-95%
- 3. Minor cytogenetic response Ph positive 36-65%

- 4. Partial cytogenetic response Ph positive 1-35%
- 5. Complete cytogenetic response Ph positive 0%
- * Major cytogenetic response = complete + partial (Ph positive ≤35%)

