6. RESPONSE DEFINITIONS

Patients will be assessed for efficacy at the end of each 28 day cycle of therapy, +/-4 days for the first 3 cycles, then 3 monthly thereafter.

6.1 Acute leukemias, MDS, CML-BP, CMML:

- 6.1.1 Complete remission: The patient must be free of all symptoms related to leukemia and have an absolute neutrophil count $\geq 1 \times 10^9 / L$ and platelet count $\geq 100 \times 10^9 / L$, and normal marrow differential ($\leq 5\%$ blasts) in a normo- or hypercellular marrow.
- 6.1.2 Partial remission: CR with 6-25% abnormal cells in the marrow or 50% decrease in bone marrow blasts.
- 6.1.3 CRp: As per CR but platelet count <100 x109/L.
- 6.1.4 Hematologic Improvement (HI)

Hematologic improvement should be described by the number of individual, positively affected cell lines (e.g. HI-E; HI-E + HI-N; HI-E+ HI-P + HI-N).

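### In Section 6.2.1 the CML platelet limits mix units and separators, so under any single reading of the dot one limit is off by a factor of 1,000; the limit that matters is the one for complete hematologic response.

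*Combined protocol and SAP*

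**What the plan says.** Section 6.2.1 of the combined protocol and SAP defines hematologic response in CML.

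- CHR, platelet item: "Platelets $\leq 450.000 \times 10^9 / L".
- NEL: "No Evidence of Leukemia (NEL) meet the same criteria as CHR except for" two items. The first is "Platelets ≥ 20.000/mm3 and < 100.000 mm3, and/or" and the second is "ANC > 500/mm3 and < 1,000/mm3".
- Composite: "Major Hematologic Response (MHR) is defined as CHR or NEL". OHR adds minor hematologic response (MiHR), which has no platelet item.

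Section 6.1, which covers acute leukemias, MDS, CML in blast phase and CMML, writes platelet limits as plain numbers in x 10^9/L, for example "CRp: As per CR but platelet count <100 x109/L". The CML platelet limits are not restated anywhere else, and the meaning of the dot is not defined.

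**The concern.** Within one short list, the platelet limits appear in two units (x 10^9/L and per mm3) with a dot before three zeros, while the neutrophil limit on the next line uses a comma for thousands. A programmer who carries one convention through the list will get one platelet limit wrong by a factor of 1,000.

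This is an operative threshold. Anti-tumor effect is the primary objective (Section 1), and Section 9.2.1 plans to estimate hematological response with 95% confidence intervals at each time point. The platelet item is also the only part of CHR that controls for thrombocytosis. If it excludes nobody, CHR and MHR can be credited to patients whose platelet count is not controlled.

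**Working it through.** **Inputs (Section 6.2.1).** CHR upper limit 450.000 x 10^9/L; NEL range 20.000 to <100.000 per mm3; NEL neutrophil range >500 to <1,000 per mm3.

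**Conversion.** 1 L = 10^6 mm3, so 1 x 10^9/L = 10^9 / 10^6 = 1,000/mm3.

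**The same reading of the dot in both lines, then the mixed reading.**

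| Reading of the dot | CHR upper limit | NEL platelet range |
|---|---|---|
| Decimal in both | 450 x 10^9/L = 450,000/mm3 (usable) | 20 to <100/mm3 = 0.02 to <0.1 x 10^9/L (not a realistic count) |
| Thousands in both | 450,000 x 10^9/L = 450,000,000/mm3 (excludes nobody) | 20,000 to <100,000/mm3 = 20 to <100 x 10^9/L (usable) |
| Decimal in CHR, thousands in NEL | 450 x 10^9/L (usable) | 20 to <100 x 10^9/L (usable) |

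The error is 450,000 / 450 = 1,000 for CHR in the second row, and 20 / 0.02 = 1,000 for NEL in the first. Only the mixed reading works for both.

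**Effect on CHR and MHR.** Take, for illustration, a platelet count of 1,500 x 10^9/L with every other CHR item met. Against 450 x 10^9/L the count is 1,500 / 450 = 3.3 times the limit, and CHR fails. Against 450,000 x 10^9/L it is 1,500 / 450,000 = 0.3% of the limit, and the patient is CHR and therefore MHR.

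**Effect on OHR.** The same patient has no peripheral blasts or promyelocytes, marrow blasts below 5%, basophils below 2% and no extramedullary involvement. MiHR requires blasts below 15%, blasts plus promyelocytes below 30%, basophils below 20%, and no extramedullary disease outside spleen and liver. It would fail only if marrow promyelocytes exceeded about 30% - 5% = 25%. The patient therefore almost always counts in OHR under either reading.

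**Effect of an unusable NEL range.** CHR has an upper platelet limit but no lower one. A patient with 60 x 10^9/L, say, who meets the other items already satisfies CHR. Losing the NEL platelet item changes the label from NEL to CHR and leaves MHR and OHR as they were. NEL also stays reachable through its neutrophil item (0.5 to 1.0 x 10^9/L).

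**Sample size (Section 9.1.1).** The chance of at least one response in 10 at a true rate of 15% is 1 - 0.85^10 = 0.803, and the half-width at n = 30 is 1.96 x sqrt(0.15 x 0.85 / 30) = 0.128. Both agree with the stated 80% and 0.13, and neither depends on the platelet limits.

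**The case against.** The best defence has two parts. First, where Section 6 writes a neutrophil count in x 10^9/L with a point, the point is a decimal (1.5 and 0.5 in Section 6.1.4.3). On that convention the CHR line already means 450 x 10^9/L. Second, the dots in the NEL line may be commas misread from the PDF. If the original has commas in NEL and a decimal point in CHR, both limits are right.

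That combination cannot be excluded from the text available, which is why the original should be checked first. It is only a partial defence. The comma in the neutrophil line directly below survived. If instead all three dots were commas in the original, the CHR limit would be 450,000 x 10^9/L and still 1,000 times too high. It is also true that few clinicians would apply such a limit literally, and that the mixed reading can be inferred from context.

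A reader might infer more than the documents support:

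- **That the notation distorts OHR.** MiHR has no platelet item, so OHR hardly moves.
- **That thrombocytopenic patients are lost as responders.** CHR has no lower platelet limit, so only their label changes.
- **That the one-in-10 expansion decision is compromised.** Section 4.2 speaks of benefit considered significant and Section 9.1.1 of at least one response. Neither names CHR, NEL or MHR, and the categories in Section 9.5.2 are not mapped to them. The link is possible but not stated.
- **That all CML patients are exposed.** Blast phase is listed under Section 6.1, where the platelet limits are clear.

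**Conclusion.** The point holds in a narrow form. As written, the CHR and NEL platelet limits in Section 6.2.1 cannot both be right under one reading of the dot, and the discrepancy is a factor of 1,000. The material exposure is the CHR limit. Under the thousands reading that the NEL line implies, it excludes nobody, and CHR and MHR could be credited to a patient with thrombocytosis who meets the other items. This applies to patients assessed under Section 6.2, mainly those in chronic phase.

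The number of patients affected cannot be estimated from the documents. It depends on how many have platelets above 450 x 10^9/L with all other items met, and on whether anyone applies the limit literally. The conclusion assumes that the dots in the available text are those of the original, or that any misreading affected both lines alike. It is a correctable error in a response threshold and does not undermine the design.

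**What to change.** Check the original document and the source response criteria. Then state every platelet and neutrophil limit in Section 6.2.1 in x 10^9/L with one notation, as Section 6.1 does. The evident intended values, subject to that check, are CHR platelets at most 450; NEL platelets at least 20 and below 100; and NEL neutrophils above 0.5 and below 1.0 (all x 10^9/L). Derive response from the corrected text.

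The cost is a few lines of text, with no change to visits, data collection or sample size.

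This does not cure a separate defect: because CHR has no lower platelet or neutrophil limit, a patient in the NEL range who meets the other items satisfies both definitions. That overlap needs its own correction.

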In study INCB 18424-132, multiple oral doses of 25 mg BID and 50 mg daily and BID have been administered with monitoring of adverse events, clinical laboratories, PK and pharmacodynamic parameters. The preliminary unaudited pharmacodynamic draft data available indicate that multiple doses of INCB018424 are able to inhibit interleukin-6 induced STAT3 phosphorylation in a dose dependent manner, similar to data obtained in the single dose studies. The data on day 1 and day 10 demonstrated similar levels of inhibition of STAT3 phosphorylation, indicating a lack of cumulative biological activity. From an evaluation of the safety data obtained in this study, the preliminary conclusion is that the INCB018424 50 mg BID dose is considered too high for healthy volunteers and patients without serious diseases. Dosing in these populations should be limited to 25 mg BID or lower and up to 50 mg daily, although higher doses than 50 daily may be safe but have not been tested beyond single doses. However, in patients with malignancies dose escalation could continue until the maximum tolerated dose is achieved due to the different benefit-risk ratio in these subjects and because these patients may respond differently.

Under IND No. 77,456, INCB018424 has also been dosed to three patients with multiple metaplasia with myelofibrosis at 25 mg BID for over five months with clinical benefit but without notable toxicity. In this study four patients have also been dosed at 50 mg INCB018424 BID but, according to protocol, dosing was halted after two of four subjects presented with significant reductions in peripheral blood neutrophils and platelets. Subsequently, according to protocol, three additional patients have been treated at the 25 mg BID dose for at least 1 month to establish this dose as the MTD in this population.

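### The CML complete hematologic response (CHR) has no lower platelet or ANC limit, so it absorbs NEL and admits patients with counts below NEL's own limits

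*Combined protocol and SAP*

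**What the plan says.** Section 6.2.1 lists seven items for CHR. Two concern blood counts, and both are ceilings: white cells no higher than the institutional upper limit, and platelets no higher than a figure printed as 450.000 x 10^9/L. The other five cover blasts and promyelocytes in blood, immature granulocytes, basophils, extramedullary disease including liver and spleen, and marrow blasts.

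The next category is introduced with "No Evidence of Leukemia (NEL) meet the same criteria as CHR except for", followed by two exceptions: "Platelets ≥ 20.000/mm3 and < 100.000 mm3, and/or" and "ANC > 500/mm3 and < 1,000/mm3". The categories then combine: "Major Hematologic Response (MHR) is defined as CHR or NEL" and "Overall Hematologic Response (OHR) is defined as CHR, NEL or MiHR". Confirmation requires the same criteria to be met again at least 28 days later, and adds no count limit.

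Section 6.1 covers acute leukemias, MDS, CMML and blast-phase CML. Its complete remission does have floors: ANC at least 1 x 10^9/L and platelets at least 100 x 10^9/L. No other section supplies a floor for CML.

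**The concern.** An exception for low counts makes sense only if CHR itself requires higher counts. NEL's upper bounds point to CHR floors of 100,000/mm3 for platelets and 1,000/mm3 for ANC, but Section 6.2.1 does not state them. Two consequences follow.

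- CHR and NEL are not separate tiers. Whoever meets NEL also meets CHR, so the CHR rate takes in patients who were evidently meant for the lesser category.
- NEL carries its own lower limits, which suggests that patients below them were meant to be in neither category. As printed, they can be CHR and therefore MHR.

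The error runs towards over-counting response. Section 9.2.1 plans 95% confidence intervals for hematological response at each time point, so those estimates could mix clean responses with severe cytopenia. Low counts are foreseeable here: Section 4.5 provides for persistent grade 4 neutropenia and thrombocytopenia, and in the earlier myelofibrosis study "dosing was halted after two of four subjects presented with significant reductions in peripheral blood neutrophils and platelets".

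**Working it through.** **The plan's own design figures.** Section 9.1.1 assumes a 0% null, a 15% target, 80% power, 10 patients first and expansion on at least one response.

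- P(at least 1 of 10 | 15%) = 1 - 0.85^10 = 0.803, which reproduces 80%.
- Half-width at n = 30: 1.96 x sqrt(0.15 x 0.85 / 30) = 0.128, which reproduces 0.13.

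These figures are not in dispute. They matter because a 0% null leaves no allowance for misclassified responses.

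**Classification check.** All other CHR items are assumed met. The printed rule is Section 6.2.1 taken literally, with either NEL range sufficient because the two are joined by and/or. The repaired rule sets CHR at platelets at least 100,000 and ANC at least 1,000. It sets NEL as not CHR, with platelets at least 20,000 and ANC above 500. Counts are per mm3.

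| Platelets | ANC | Printed | MHR as printed | Repaired | MHR repaired |
|---|---|---|---|---|---|
| 200,000 | 2,000 | CHR | yes | CHR | yes |
| 60,000 | 2,000 | CHR and NEL | yes | NEL | yes |
| 200,000 | 700 | CHR and NEL | yes | NEL | yes |
| 60,000 | 700 | CHR and NEL | yes | NEL | yes |
| 10,000 | 2,000 | CHR | yes | neither | no |
| 200,000 | 300 | CHR | yes | neither | no |
| 10,000 | 300 | CHR | yes | neither | no |
| 60,000 | 300 | CHR and NEL | yes | neither | no |
| 10,000 | 700 | CHR and NEL | yes | neither | no |

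Rows 2 to 4 show the overlap: the CHR count changes and the MHR count does not. Rows 5 to 7 are in neither NEL range, yet score CHR and MHR. Rows 8 and 9 have one count in a NEL range and the other below its limit. The and/or wording literally admits them to NEL as well, which is why the repair must require both lower limits.

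**Overall response.** MiHR has no count floor. A patient who meets the remaining CHR items will almost always meet MiHR too; the one item CHR does not cover is promyelocytes in the marrow. The overall rate is therefore almost unaffected.

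**Illustration for the expansion rule.** Suppose that CHR or MHR is the counted response, that all 10 CML patients are scored under 6.2, and that none truly responds. Let q be the share who qualify only through the missing floors. The documents give no value for q, so a range is shown. The chance of a false expansion is 1 - (1 - q)^10.

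| Assumed q | Calculation | Chance of at least one |
|---|---|---|
| 1% | 1 - 0.99^10 | 9.6% |
| 2% | 1 - 0.98^10 | 18.3% |
| 5% | 1 - 0.95^10 | 40.1% |
| 10% | 1 - 0.90^10 | 65.1% |

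Under the stated null the chance is 0%.

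**The case against.** A careful reader can infer the floors from NEL's wording, and Section 9.2.1 calls the efficacy analyses exploratory. Both points are fair. They limit the weight of the problem, but a response definition should not depend on inference. Several stronger readings are tempting, and the documents do not support them.

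- *Severe cytopenia by itself is scored as CHR.* It is not. The patient must also clear the blast, promyelocyte, immature-cell, basophil, organ and marrow items.
- *All CML patients are affected.* Blast-phase CML is listed under 6.1, where complete remission has floors. The gap falls mainly on other CML.
- *The drug's known cytopenia shows the problem will be common.* The two-of-four observation was at 50 mg BID in myelofibrosis, and Section 4.1 does not allow chronic-phase CML patients to escalate to that dose. At 25 mg BID, Section 2.2.3 reports no notable toxicity in three patients over five months. These numbers are small and Section 4.5 does anticipate cytopenia, so misclassification is plausible but its frequency is unknown.
- *A misclassified patient opens the expansion.* Section 4.2 speaks of significant benefit, Section 9.1.1 of response, and Section 9.5.2 of generic complete and partial response. None names CHR or MHR. If overall hematologic response were counted, adding floors to CHR would hardly change the decision, because MiHR has none.
- *The platelet ceiling is 1,000 times too high.* That follows only if the dot is a thousands separator, as in the NEL platelet limits. The NEL neutrophil limit uses a comma, so notation is mixed. Read as a decimal, the printed value is 450 x 10^9/L. It is ambiguous, not shown to be wrong.
- *CHR is the best CML response.* It is only the top hematologic tier; Sections 6.2.2 and 6.2.3 define cytogenetic and molecular response separately.

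**Conclusion.** The point holds as a defect in a stated rule. As printed, NEL is contained in CHR, MHR equals CHR, and patients with platelets below 20,000/mm3 or ANC at or below 500/mm3 who meet every other CHR item are counted as CHR and MHR. This follows from the text alone and needs no assumption about rates.

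The size is not known. The CHR rate is inflated by every patient in the NEL ranges and by those below them; the MHR rate only by patients with a count below a NEL limit; the overall rate hardly at all. The 9.6% to 65.1% range for a false expansion rests on three assumptions: the chosen values of q, all 10 CML patients being scored under 6.2, and CHR or MHR being the counted response. It shows how sensitive a one-in-ten rule with a 0% null is, and is not a forecast.

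**What to change.** In Section 6.2.1:

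1. Add to CHR platelets of at least 100,000/mm3 and ANC of at least 1,000/mm3. These are NEL's own upper bounds, and they match complete remission in Section 6.1.
2. Define NEL as all other CHR items met, one or both counts below the CHR floors, and both platelets at least 20,000/mm3 and ANC above 500/mm3. CHR and NEL are then mutually exclusive. State that counts below either NEL limit are neither CHR nor NEL.
3. Print the platelet ceiling as 450 x 10^9/L and use one number notation throughout the section.

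In Sections 4.2, 9.1.1 and 9.5.2, name the CML category that counts as a response for the expansion rule. Without this, the new floors may not affect that decision.

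The cost is a few lines of text. The counts are already collected under the study calendar, and dosing and visits are unchanged. The CHR rate, and possibly the MHR rate, may come out slightly lower. The change is best made before CML responses are scored.

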3.1 Inclusion Criteria

- A. Must be at least 18 years of age.
- B. Patients must have relapsed/refractory leukemias for which no standard therapies exist. Patients with poor-risk myelodysplasia (MDS) [i.e. refractory anemia with excess blasts (RAEB-1 or RAEB-2) by WHO classification] and chronic myelomonocytic leukemia (CMML) who failed prior therapy are also candidates for this protocol. Relapsed/refractory leukemias include acute non-lymphocytic leukemia (AML) by WHO classification (i.e. ≥ 20% blasts), acute lymphocytic leukemia (ALL), or chronic myelogenous leukemia (CML) in blast crisis. Patients with CML who are resistant to at least two tyrosine kinase inhibitors and have no standard stem cell transplant option are also eligible.
- C. ECOG performance status of 0-2.
- D. A female of childbearing potential must have a negative serum or urine pregnancy test at screening. Women of child-bearing potential (i.e., women who are premenopausal or not surgically sterile) must use acceptable contraceptive methods (abstinence, intrauterine device [IUD], oral contraceptive or double barrier device), and must have a negative serum or urine pregnancy test within 2 weeks prior to beginning treatment on this trial. Sexually active men must also use acceptable contraceptive methods for the duration of time on study.

- E. Must be able and willing to give written informed consent.
- F. In the absence of rapidly progressing disease, the interval from prior treatment to time of study drug administration should be at least 2 weeks for cytotoxic agents, or at least one week for noncytotoxic agents. Persistent clinically significant toxicities from prior chemotherapy must not be greater than grade 2.
- G. Patients must have the following clinical laboratory values unless considered due to leukemic organ involvement:
 - 1. Serum creatinine ≤ 2.0 mg/dl.
 - 2. Total bilirubin ≤ 1.5x the upper limit of normal unless considered due to Gilbert's syndrome or hemolysis.
 - 3. Alanine aminotransferase (ALT), and aspartate aminotransferase (AST) \leq 2.5x the upper limit of normal unless considered due to organ leukemic involvement (then \leq 5x the upper limit of normal).
 - H. Patients with active CNS disease are included and will be treated concurrently with intrathecal therapy. INCB018424 will not be administered by intrathecal route.

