9.1.1 Selection of Sample Size

This phase II study will use a Gehen's design. Assuming a null response rate of 0%, targeting a 15% response rate and power=80%, the trial will initially enroll 10 patients in each disease category: 1) AML; 2) ALL; 3) MDS; and 4) CML. If at least one response is achieved in the 10 patients in a disease

Category, then a total of 30 patients will be enrolled in this disease category. Thirty patients will provide a confidence interval for response rate with half-width=0.13, assuming the true response rate is 15%. The total sample size is 120.

For toxicity evaluation, patients enrolled in the study will be considered in 2 cohorts (I) those with relapsed/refractory AML, ALL, and MDS (including CMML), and blast phase CML, and (II) those with chronic phase CML. At any time after 6 patients are enrolled in cohort I (including AML, ALL, MDS, blast phase CML patients), if 30% or more patients experience grade 3 or 4 toxicity thought to be directly related to INCB018424 and lasting longer than 2 weeks, then we will stop that cohort of the trial. At any time after 6 patients are enrolled in cohort II (including chronic phase CML patients), if 15% or more patients experience grade 3 or 4 toxicity thought to be directly related to INCB018424 and lasting longer than 2 weeks, then we will stop that cohort of the trial.

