9.2.1 Efficacy and PK/PD Analysis

Efficacy analyses will be exploratory in nature. All efficacy measures will be estimated with 95% confidence intervals at the dose used in the expanded cohort. The clinical response and the hematological response will be estimated with 95% confidence intervals at each time point. The response rates over time may be analyzed graphically or using a statistical model.

The PK parameters of INB018424 will be summarized using descriptive statistics, and the log-transformed INCB018424 PK parameters will be compared using a 1-factor analysis of variance. The mean values of the PK parameters may be compared to historical data in healthy volunteers to determine if the INCB018424 PK profile is different between patients with hematological malignancies and healthy patients.

For each patient who has taken study medication, the PD parameters will be calculated to explore preliminary evidence of PD activity by assessing the

effect of INCB018424 on pre- and post-dose. If the p-STAT3/5 signaling data are sufficiently robust, an exploratory PK/PD analysis will be performed.

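### CML response in Section 6.2 is defined by absolute on-study levels with no comparison to baseline, so unchanged chronic-phase disease can be scored as a hematologic or cytogenetic response

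*Combined protocol and SAP*

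**What the plan says.** Section 6.2.1 builds hematologic response in CML from three grades: complete hematologic response (CHR), no evidence of leukemia (NEL) and MiHR. "Overall Hematologic Response (OHR) is defined as CHR, NEL or MiHR". MiHR has four conditions, all of them ceilings. The first is "< 15% blasts in BM and in PB". The others are blasts plus promyelocytes below 30%, peripheral basophils below 20%, and no extramedullary disease beyond spleen and liver. A response is confirmed if the criteria still hold 28 days or more after they were first satisfied.

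Section 6.2.2 assigns cytogenetic response by the Ph-positive percentage found on study. The lowest response band is "Minimal cytogenetic response Ph positive 66-95" (percent).

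Section 3.1 B admits "Patients with CML who are resistant to at least two tyrosine kinase inhibitors and have no standard stem cell transplant option". Section 4.1 describes these patients as chronic phase and assesses them after 3 months. Sections 4.1 and 9.1.1 give them their own toxicity cohort (II).

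On analysis, 9.2.1 says "The clinical response and the hematological response will be estimated with 95% confidence intervals at each time point", and 9.2 lists cytogenetic response as an efficacy variable. On expansion, 9.1.1 says "Assuming a null response rate of 0%, targeting a 15% response rate and power=80%, the trial will initially enroll 10 patients" in each of four disease categories, CML being one. "If at least one response is achieved in the 10 patients in a disease" category, that category goes to 30 patients. Section 4.2 words the trigger differently, as one patient with benefit judged significant. Section 9.5.2 classifies every patient as complete response, partial response, stable disease, progressive disease, early death or unknown, and does not map these to the grades in 6.2.

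**The concern.** A response category should record something that happened after treatment started. MiHR is meaningful for a patient who enters in blast phase and returns to chronic phase. For a patient who enters in chronic phase, it describes the starting point. Section 6.1 already covers blast-phase CML, so 6.2 falls mainly on the chronic-phase patients for whom MiHR says least.

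The primary objective is to observe anti-tumor effect. If unchanged disease is scored as response, the chronic-phase OHR rate cannot serve that objective, whatever its confidence interval. The 0% null rate in 9.1.1 also depends on what is counted: it is reasonable for a response that requires change, but not for a state that patients can hold at entry.

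**Working it through.** **1. Is a baseline comparison supplied anywhere?**
- 6.2.1: MiHR has only ceilings, with no white-cell, platelet or spleen-size condition. CHR and NEL are also absolute states.
- 6.2.1, confirmation: persistence only. Disease that does not change satisfies it.
- 6.2.2: the text speaks of suppression of the Ph chromosome, which hints at change, but the bands are levels. Read literally, a patient entering at 95% Ph-positive or less is already in a response band. One entering at 40% is in the minor band, and one at 30% is in the partial band, hence major.
- 3.1 B: no minimum disease burden, and no exclusion of a patient already in a response category.
- 6.1.4, by contrast: hematologic improvement requires a pretreatment deficit or transfusion dependence, plus a gain. The plan uses baseline there and not in 6.2.

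**2. The plan's own figures (9.1.1) reproduce.**
- Chance of at least 1 response in 10 at a true rate of 15%: 1 − 0.85^10 = 0.803. With 9 patients it is 0.768, so 10 is the smallest number reaching 80%.
- Half-width at n = 30: 1.96 × √(0.15 × 0.85 / 30) = 0.128, which rounds to the stated 0.13.

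**3. Effect on the OHR estimate.** Suppose all 10 CML patients enter within the MiHR limits and remain there on an inactive drug. OHR is then 10/10, with exact 95% lower limit 0.025^(1/10) = 0.69 and upper limit 1. This does not depend on the expansion rule.

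**4. Effect on the expansion rule, if OHR is the counted response.** Let f be the share of the CML arm meeting MiHR at entry and s the chance that such a patient still meets it at assessment. The documents give neither, so both are assumptions. With an inactive drug and independent patients:

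P(at least 1 of 10) = 1 − (1 − f × s)^10

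| f | s | f × s | P(pass) | Expected in 30 (30 × f × s) |
|---|---|---|---|---|
| 0.10 | 1 | 0.10 | 65.1% | 3 |
| 0.20 | 1 | 0.20 | 89.3% | 6 |
| 0.50 | 1 | 0.50 | 99.9% | 15 |
| 0.10 | 0.5 | 0.05 | 40.1% | 1.5 |
| 0.20 | 0.5 | 0.10 | 65.1% | 3 |
| 0.50 | 0.5 | 0.25 | 94.4% | 7.5 |

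At f × s = 0.15 (for example f = 0.3, s = 0.5), an inactive drug passes with probability 80.3%, the same as a drug with the 15% rate the design targets. A false pass commits 20 more patients.

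**5. Cytogenetic response.** The size of the effect depends on the distribution of Ph percentage at entry, which the documents do not give. No figure can be attached.

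**The case against.** The best counter-argument is that the plan has other filters. Section 4.2 expands only on benefit judged significant, and a patient unchanged since entry shows none. Section 4.1 separates responding patients from those with stable disease, and 9.5.2 has a stable-disease category that such a patient fits. Section 9.2.1 calls the efficacy analyses exploratory, and no test is planned on OHR. The component grades are defined separately, so an OHR rate driven by MiHR could be recognised. Only the chronic-phase part of one of four categories is affected.

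Much of this stands against the stronger readings. A reader might infer that one chronic-phase patient opens expansion with certainty and that the 0% null is therefore false. The documents do not support that. No section says that OHR is the response counted in 9.1.1. If only CHR or NEL counts, the effect is much smaller, although a patient already in CHR at entry is still not excluded. Even if OHR counts, a single such patient passes the rule with probability s, not 1, because scoring takes place on study and some patients may progress or be unassessable by then.

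A reader might also infer that every chronic-phase patient meets MiHR at entry. The plan does not define chronic phase. The statement rests on the ordinary meaning of the term, and typically is as far as it goes.

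The objection does not repair the definition. An unchanged chronic-phase patient is stable disease under 9.5.2 and can be an OHR responder under 6.2.1, and nothing says which prevails. The exploratory label does not make an estimate of entry state informative about the drug.

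**Conclusion.** The point holds as a faulty rule and not merely as missing detail: applied as written, 6.2 lets unchanged disease count as response in chronic-phase CML. The direct consequence is for the hematologic response estimates in 9.2.1, up to 10/10 (69% to 100%) on an inactive drug in the limiting case where all ten patients start and stay within the MiHR limits. It rests on the text of 6.2 and on the ordinary meaning of chronic phase.

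The consequence for expansion is conditional on OHR being the counted response and on the assumed f and s. It ranges from 40.1% to 99.9% over the values tabulated. The cytogenetic consequence is a possibility of unknown size.

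**What to change.** - In 6.2, count a hematologic or cytogenetic response only if the category is better than the one the patient held at baseline.
- In 6.2.1, score MiHR, and OHR reached through MiHR, only for patients whose baseline exceeds the MiHR limits.
- In 9.1.1, name the CML response grade that counts for expansion, and align 4.2 and 9.5.2 with it.

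With these changes, unchanged disease cannot be counted, the 0% null can stand, and the stated sample sizes need no revision.

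The cost is a few sentences and a lower chronic-phase hematologic response rate. Patients who enter in CHR can contribute only to cytogenetic response. The change is not purely editorial. Table 5.1 asks for screening cytogenetics only where indicated, so a baseline Ph percentage must be made a requirement for every CML patient, and those without one are not evaluable for cytogenetic response. Table 5.1 also lists the screening blood count without naming a differential. Baseline peripheral blasts, promyelocytes and basophils should be stated as required, so that the MiHR limits can be checked at entry.
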